Fixed-Dose Netupitant and Palonosetron for Chronic Nausea and Vomiting in Cancer Patients

Principal Investigator: [name]
Co-Principal Investigator: [name]
Collaborators: [name], [name], [name], [name]
[name], [name], [name], [name], [name]
[name]
Biostatistics Collaborators: [name], [name]

Table of Contents

A. Study Objectives	2
B. Background	2
C. Pharmaceutical Information	5
D. Experimental Approach	7
E. Patient Withdrawal Criteria	13
F. Investigator Communications with Helsinn	
G. Serious Adverse Events Reporting	16
H. Statistical Considerations	17
I. Data Confidentiality Procedures	
J. References	

A. Study Objectives

Primary objective:

To estimate the efficacy (i.e. change in nausea numeric rating scale [NRS] from baseline between day 5-15) of fixed dose netupitant and palonosetron (NEPA) for chronic nausea in cancer patients.

Secondary objective:

- 1. To assess the secondary outcomes (e.g. proportion of patients who achieved their personalized nausea goal, antiemetic use, nausea episodes duration/frequency) for NEPA vs. placebo.
- 2. To assess the adverse effects associated with NEPA and placebo.

B. Background

B.1. Significance of Chronic Nausea in Cancer Patients. Nausea is defined as "an unpleasant sensory and emotional experience, which may be described in terms of a sick feeling with or without a sense of impending vomiting/retching - often associated with a perception of epigastric or upper abdominal unpleasantness or awareness".¹ Chronic nausea is defined as nausea of 1 month or greater.^{2,3} In one systematic review of 39 studies consisting of 24263 patients with incurable cancer, nausea occurred in 31% (95% confidence interval [CI] 27-35%) of patients, and vomiting in 20% (95% CI 17-22%).⁴ In another systematic review of far advanced cancer patients, the prevalence of nausea was estimated to be 6-68%.⁵ Rhondali et al. reported that among 444 cancer patients seen at the supportive care clinic at MD Anderson Cancer Center, 112 patients had moderate/severe chronic nausea of >=4/10 in intensity.⁶ 68/112 (61%) patients had a response (defined as 30% improvement from baseline) to the multimodal therapies offered by the palliative care team (e.g. metoclopramide, ondansetron, other anti-emetics, constipation management, counseling) at the followup visit 2 weeks later.

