- 2. Clinical evidence of bowel obstruction at the time of study enrollment
- 3. Expected to use other 5HT3 antagonists or NK1 antagonists for prophylaxis during the study
- 4. Continuation of over-the-counter therapies for nausea and/or vomiting during the study
- 5. On cytotoxic chemotherapy in the high/moderate/low emetogenic risk categories or oral antineoplastic agents in the high or moderate emetogenic risk categories according to the latest NCCN guideline within 2 weeks of study enrollment
- 6. On scheduled potent CYP3A4 inducers at the time of study enrollment (avasimibe, carbamazepine, phenytoin, rifampin, efavirenz, nevirapine, barbiturates, systemic glucocorticoids, modafinil, oxcarbazine, phenobarbital, pioglitazone, rifabutin, St. John's wort, troglitazone)¹
- 7. On scheduled CYP3A4 substrates with narrow safety range at the time of study enrollment (alfentanil, cyclosporine, dihydroergotamine, ergotamine, pimozide, quinidine, sirolimus, tacrolimus)
- 8. On scheduled strong or moderate CYP3A4 inhibitors (boceprevir, clarithromycin, conivaptan, indinavir, itraconazole, ketoconazole, lopinavir/ritonavir, mibefradil, nefazodone, nelfinavir, posaconazole, ritonavir, saquinavir, telaprevir, telithromycin, voriconazole; amprenavir, aprepitant, atazanavir, ciprofloxacin, darunavir/ritonavir, diltiazem, erythromycin, fluconazole, fosamprenavir, grapefruit juice, imatinib, verapamil) within one week of study enrollment¹
- 9. Unwilling to provide informed consent
- 10. Severe renal impairment (calculated Creatinine clearance <=29 cc/min)²
- 11. Severe liver impairment (Child-Pugh Score >9)³
- 12. Females who are pregnant, lactating, or intend to become pregnant during the participation of the study; childbearing age women who are not on birth control. Positive pregnancy test for women of childbearing potential, as defined by intact uterus and ovaries, and no history of menses within the last 12 months. Pregnancy test to be performed on the day of enrollment. In cases of women with elevated b-HCG, these candidates will be eligible to participate so long as the level of b-HCG is not consistent with pregnancy and the non-pregnant status is confirmed by a Gynecologic examination.

¹ according to FDA website

http://www.fda.gov/Drugs/DevelopmentApprovalProcess/DevelopmentResources/DrugInteractionsLabelin g/ucm093664.htm

² Calculated creatinine clearance can be done within 14 days of study enrollment.

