basis. They will be asked not to take other anti-emetics (e.g. haloperidol, olanzapine, corticosteroids, antihistamines, anticholinergics) unless (1) they have already been using them on a scheduled basis for an indication other than nausea or (2) if metoclopramide is ineffective or intolerable, in which case they may use them as prescribed previously for rescue purposes. Metoclopramide will be provided free of charge to patients requiring rescue medication. All antiemetic medications during the study will be documented.

To minimize constipation, all patients will be advised to take a laxative regimen (e.g. senna 1-4 tablets BID, PEG 17 g PO BID PRN) prophylactically if they are on opioids and/or report any constipation symptoms.

D.9. Stopping rules. Patients who had a significant placebo response (see Section D.4) by day 4(+/-1) will not continue. Patients may also withdraw from study anytime and pursue standard of care. Patient dropouts prior to the administration of drug or placebo will be replaced.

D.10. Study assessments. See Table 4 for a detailed description of all study assessments.

Nausea numeric rating scale (primary outcome): To evaluate the efficacy of NEPA/placebo, each patient will complete a diary daily from time of enrollment through the end of study documenting the average intensity of nausea over the preceding 24 h and over the past 5 days at Baseline and on or about Days 5, 10, 15, 20, and 25 using a 0-10 NRS (where 0=no nausea and 10=worst possible. This scale has been used in multiple studies.^{6,23} The primary efficacy endpoint is change in nausea intensity from day 5 to day 15. The minimal clinically important difference is 1 point.³⁶

Secondary endpoints:

- Worst intensity of nausea—highest score over the preceding 24 h using a 0-10 NRS (where 0=no nausea and 10=worst possible).
- Number of doses of rescue antiemetic (i.e. metoclopramide) and total dose over the past 24 hours.
- Index of nausea and vomiting and retching (INV-R)—this validated questionnaire consists of 8 items asking about the patient's experience regarding nausea and vomiting over the past 12 hours. Each item includes a 5-point Likert scale (0-4 points) with descriptive words. The concurrent validity is 0.83-0.87, and Cronbach's alpha was 0.89-0.97.³⁷⁻³⁹ The total score ranges from 0 to 32 points, with a higher score indicating more nausea/vomiting.

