- Proportion of patients with complete response—defined as no significant nausea (average NRS≤2), no rescue medication for nausea/vomiting and no emesis. A vomiting episode is defined as a single vomiting episode (defined as expulsion of stomach contents), a single retching (defined as an effort to vomit without expulsion of stomach contents) or any retching combined with vomiting.^{27-29,31}
- Global symptom evaluation we will assess impression of change by asking them about their nausea and vomiting (worse, about the same, or better; If better, how

much better? Hardly any better, a little better, somewhat better, moderately better, a good deal better, a great deal better, a very great deal better; If worse, how much worse? Hardly any worse, a little worse, somewhat worse, moderately worse, a good deal worse, a great deal worse, a very great deal worse) comparing between the level of nausea and vomiting days 1-5 vs. days 6-15. Study satisfaction will be assessed with the following questions, "Was it worthwhile for you to participate in this research study?", "If you had to do it over, would you participate in this research study?", "Did your quality of life get better by participating in this research study?", "Did your quality of life get worse by participating in this research study?" Blinding will be assessed by asking patients and study staff which group assignment they believe they received: "NEPA", "placebo", or "do not know".

- Personalized Nausea Goal—we will assess personalized nausea goal by asking "At what level of intensity would you feel comfortable? 0-10 where 0=no nausea and 10=worst possible". Personalized nausea response is defined as nausea NRS ≤ personalized nausea goal. To assess stability of personalized nausea goal, we will be asking participants to provide this on day 15±2 as well.

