* Assessments may be done over the phone or in person from day 1 to day 15±2, and on day 20±2 and 25±2. For the other days starting day 16 (open label phase), patients will continue to complete assessments in the diary on their own until the end of study.

¹ Optional extension phase

² patient initials, medical record number, date of birth, sex, race, education, marital status, cancer diagnosis, stage, co-morbidities, cause(s) of nausea, date of last cancer treatment, Karnofsky Performance status, Memorial Delirium Assessment Scale (MDAS).⁴¹

³ all scheduled and as needed medications that could be used to treat nausea, such as metoclopramide, haloperidol, olanzapine, corticosteroids, 5HT3 antagonists, antihistamines, anticholinergics will be documented.

⁴ To evaluate the efficacy of NEPA/placebo, each patient will complete a diary from time of enrollment through the end of study documenting the average intensity of nausea over the preceding 24 h using a 0-10 NRS (where 0=no nausea and 10=worst possible), the worst intensity of nausea over the preceding 24 h using the same 0-10 NRS (where 0=no nausea and 10=worst possible), the number of doses of rescue antiemetic (i.e. metoclopramide) and total dose over the past 24 hours, and the Index of nausea and vomiting and retching (see Section D.10).

⁵ validated questionnaire that measures 9 other common symptoms in the past 24 hours (pain, fatigue, nausea, depression, anxiety, drowsiness, shortness of breath, appetite, sleep, and feeling of well-being) using numeric rating scales.⁴²

⁶ we will assess personalized nausea goal by asking "At what level of intensity would you feel comfortable? 0-10 where 0=no nausea and 10=worst possible" ⁴⁰. Personalized nausea response is defined as nausea NRS \leq personalized nausea goal. To assess stability of personalized nausea goal, we will be asking participants to provide this on day 15±2 as well.

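### The rescue endpoint counts metoclopramide only, although D.8 permits other rescue antiemetics, so rescue use is understated in the patients whom metoclopramide fails

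*Combined protocol and SAP*

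**What the plan says.** Secondary objective 1 (Section A) covers "proportion of patients who achieved their personalized nausea goal, antiemetic use, nausea episodes duration/frequency) for NEPA vs. placebo". The outcome there is antiemetic use in general.

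Section D.10 turns it into a narrower endpoint: "Number of doses of rescue antiemetic (i.e. metoclopramide) and total dose over the past 24 hours". Footnote 4 to Table 4 repeats the restriction for the daily diary: "the number of doses of rescue antiemetic (i.e. metoclopramide) and total dose over the past 24 hours".

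Section D.8 asks patients to avoid other antiemetics, but with exceptions: "They will be asked not to take other anti-emetics (e.g. haloperidol, olanzapine, corticosteroids, antihistamines, anticholinergics) unless". The exception that matters here is "if metoclopramide is ineffective or intolerable, in which case they may use them as prescribed previously for rescue purposes". D.8 also states: "All antiemetic medications during the study will be documented".

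Complete response, also in D.10, carries a rescue component that is not tied to one drug: "no rescue medication for nausea/vomiting and no emesis".

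Section H names no specific analysis for the rescue endpoint, and no section says how a switch from metoclopramide to another agent is to be scored.

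**The concern.** The parenthesis in D.10 and footnote 4 restricts the count; it does not give an example. D.8 then opens a second route to rescue for precisely those patients in whom metoclopramide does not work or cannot be taken. Doses taken by that route are rescue by the protocol's own description, but they fall outside the endpoint.

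The loss is therefore not random. It falls on patients whom metoclopramide fails, and it makes them look as if they needed less rescue. Section D.1 says that the study exists to determine the effect size in each arm for a later confirmatory trial. An arm-level rescue estimate that is too low would be carried into that planning whether or not the arms are formally compared.

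**Working it through.** **The plan's own figure.** The only power figure in the document concerns the primary endpoint. With n = 20, a difference of 2 and an SD of 2.5 (Section H), the effect size is 2/2.5 = 0.8. A two-sided paired t-test at 0.05, with 19 degrees of freedom and noncentrality 0.8 × √20 = 3.58, has power 92.4%, against the stated 92%. It reproduces, and nothing below touches it. The plan gives no figure for rescue use.

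**Reading the definitions together.** Three patients who all use rescue permitted by D.8 are scored as follows.

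| Patient | Doses actually taken | Counted under D.10 |
|---|---|---|
| Stays on metoclopramide | all metoclopramide | all |
| Replaces it, wholly or partly | metoclopramide, then or alongside another agent | metoclopramide part only; the count falls |
| Adds a second agent, same metoclopramide | metoclopramide plus the other agent | metoclopramide part only; the count does not fall but is too low |

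**One patient (assumed need).** Take 3 rescue doses a day over the 10 blinded days (length from D.1): 3 × 10 = 30 doses. With a full switch after day k, the scored total is 3 × k:
- k = 8: 24
- k = 5: 15
- k = 2: 6
- switch from the start: 0

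With 30 evaluable patients at 2:1 (Section H) there are about 10 on placebo and 20 on NEPA. One such patient who switches from the start lowers the arm mean by 3/10 = 0.30 doses a day on placebo, or 3/20 = 0.15 on NEPA.

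**Between arms (all inputs assumed).** Let true rescue be 2.0 doses a day on placebo and 1.0 on NEPA, and let p and q be the uncounted shares on placebo and NEPA. The measured difference is 2.0 × (1 − p) − 1.0 × (1 − q), and the true difference is 1.0.

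| p | q | Measured difference |
|---|---|---|
| 20% | 5% | 1.60 − 0.95 = 0.65 |
| 20% | 10% | 1.60 − 0.90 = 0.70 |
| 40% | 5% | 1.20 − 0.95 = 0.25 |
| 40% | 10% | 1.20 − 0.90 = 0.30 |

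The range is 0.25 to 0.70, a loss of 30% to 75%.

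**The opposite pattern.** If the uncounted doses are more numerous on NEPA, the sign of the error changes. With p = 5% and q = 40%, the measured difference is 1.90 − 0.60 = 1.30, an overstatement of 30%.

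**When the sign of the difference would reverse.** This needs 2.0 × (1 − p) < 1.0 × (1 − q), that is p > 0.5 + q/2. For q of 5% to 10%, p must exceed 52.5% to 55%.

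**The case against.** Much can be said for the plan. D.8 requires every antiemetic to be documented and says that medication use goes into the diary, and the diary row of Table 4 lists rescue medications without limiting them. The data may well exist, and the gap could be closed at analysis. Restricting total dose to one drug also has a reason: milligrams of different drugs cannot be added. Finally, Section H says that comparing NEPA with placebo is not an objective, and the endpoint is secondary in a proof-of-concept study.

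The point about milligrams stands and shapes the fix. The point about documentation stands in part. Recording a drug is not a rule for scoring it, and a rule chosen after the data are seen is post hoc. Footnote 4 specifies a daily count for metoclopramide only; the diary form (Appendix B) is not in the text available, so whether it captures counts for other agents cannot be judged. The point about comparison limits the consequence but does not remove it: arm-level estimates are also too low, and secondary objective 1 does set NEPA against placebo.

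A reader might infer that the rescue endpoint and complete response contradict each other. They do not. One is a dose count and the other a yes/no composite, and the composite already covers any rescue drug, so a patient who switches cannot be scored a complete responder.

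A reader might also infer that rescue with a drug of the same class as the study treatment is allowed and goes uncounted, because the exclusion criterion reads "Expected to use other 5HT3 antagonists or NK1 antagonists for prophylaxis during the study" and the list in D.8 is only illustrative. The wording leaves this open, but no section expressly permits such rescue.

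**Conclusion.** The point holds as a defect of definition. The stated count leaves out rescue that the protocol itself allows, and it does so selectively, in patients whom metoclopramide fails or who cannot tolerate it. This follows from the text alone and rests on no assumption.

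Its size does not follow from the text. The documents give no rescue or switch rates, so the illustrative range of 0.25 to 0.70 against a true 1.0 rests wholly on the assumed figures. The direction between arms is also unknown. More switching on placebo would understate a NEPA benefit, but intolerance of metoclopramide need not track response to the study drug, and larger losses on NEPA would overstate the benefit.

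Two stronger readings are not supported. One is that the worst-controlled patients drop to zero counted doses: this needs full replacement before any metoclopramide dose is counted, whereas D.8 allows the switch only after metoclopramide has proved unsuitable, so some doses would often be counted. The other is that the NEPA-placebo difference could reverse: under the assumed true rates, more than half of placebo rescue doses would have to go uncounted, well above the 20-40% illustrated.

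The primary endpoint, its power and complete response are unaffected.

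**What to change.** The definition is wrong as written and should be changed in D.10 and in footnote 4 to Table 4:
- Define rescue use as any antiemetic taken as needed for nausea or vomiting.
- Report it as days with any rescue and as number of rescue doses of any agent.
- Keep metoclopramide total dose as a separate descriptive measure.
- Confirm that the diary records a daily dose count for every rescue agent, not only metoclopramide.

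The cost is wording in two places, a check of the diary form and a small amount of analysis work, since D.8 already calls for all antiemetics to be documented. The change concerns measurement only and alters nothing that patients may take.
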